7.3 LOST TO FOLLOW-UP

A participant will be considered lost to follow-up if he or she fails to attend 3 consecutive scheduled visits (either telehealth or in person) and is unable to be contacted by the study site staff.

The following actions must be taken if a participant fails to return to the clinic for a required study visit:

- The site will attempt to contact the participant and reschedule the missed visit within 1 day and counsel the participant on the importance of maintaining the assigned visit schedule and ascertain if the participant wishes to and/or should continue in the study.
- Before a participant is deemed lost to follow-up, the investigator or designee will make every effort to regain contact with the participant (where possible, 3 telephone calls and, if necessary, a certified letter to the participant's last known mailing address or local equivalent methods). These contact attempts should be documented in the participant's medical record or study file.
- Should the participant continue to be unreachable, he or she will be considered to have withdrawn from the study with a primary reason of lost to follow-up.

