9.4.2 ANALYSIS OF THE PRIMARY EFFICACY ENDPOINT(S)

The primary endpoint of this clinical trial is the estimate of the median time to sustained clinical response for the treatment and placebo arms. Kaplan-Meier method will be used to estimate the time to sustained clinical response distribution and log-rank test will be utilized to compare the time to sustained clinical response distributions between the two study arms. Events will be defined as cases that attain clinical response while on the follow-up window and time to event will be calculated as the days from symptom onset to the resolution of symptoms to zero based on the Modified FLU-PRO Plus questionnaire. Patients who do not attain to clinical response while on the follow-up window will be censored on Day-21 or on the day they are off study before Day-21 due to other reasons. Although all analyses will be conducted based on the intent-to-treat context, sensitivity analyses based on the adherence to the protocol regimen will also be carried out for the primary as well as secondary objectives.

When appropriate, Last-Value-Carried-Forward (LVCF) imputation approach will be utilized for the missing values. As this is a small study that has a short span of enrollment and treatment windows, we do not anticipate excessive missing values; however, missingness structure will still be analyzed as to whether or not the missingness is Missing Completely at Random (MCAR), or Missing at Random (MAR), or Not-Missing at Random (NMAR). In the even of MCAR and MAR, sensitivity analyses will be carried out by using Multiple Imputation (MI) techniques.

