# BOSS-Covid-19 Study (BOSS-001)

at least three days. Time to sustained clinical response will be calculated from the date of testing to the first day all symptoms are  $\leq 2$ .

Power calculation will be based only on the first primary objective of the trial. Based on the median time to sustained clinical response reported by CDC [122], the expected median time to response in the placebo arm will be approximately 16 days from the onset of symptoms in outpatients. With a sample size of 20 in each arm, a difference in median time to sustained clinical response of 10 days between the intervention arm and the placebo arm will be able to be detected with 81.5% statistical power with 5% Type-1 error rate. Median time to sustained clinical response will be estimated based on 21-day follow-up. With an attrition expectation of around 20%, the planned accrual is 26 patients in each arm and potentially up to 30 patients.

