# BOSS-Covid-19 Study (BOSS-001)

days. Participants will receive the full study supply (14-day medication) at randomization. Study capsules should be stored at ambient temperature (15°C to 25°C), away from direct sunlight. The study is double blinded; all subjects, investigators, and study personnel involved in the conduct of the study, including data management and primary biostatistician, will be blinded to treatment assignment. There will be an independent unblinded statistician. The unblinded study statistician will not otherwise participate in study procedures or data analysis.

A randomization list will be prepared by the unblinded statistician and provided to the investigational product (IP) depot for labelling. Sponsor and CRO study staff will remain blinded to study treatment. Randomization numbers will be assigned through the Electronic Data Capture (EDC) system.

Participants will complete a daily questionnaire on Covid-19 symptoms, which will be used to determine the primary endpoint for the study. For this reason, it is important that participants remain blinded to treatment allocation.

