# BOSS-Covid-19 Study (BOSS-001)

## 5.3.2 Primary Analyses

Primary estimand-1 is defined to be the difference of median time to sustained clinical response between participants taking 3 g TQ Formula (500 mg per capsule, 3 capsules BID) and participants taking placebo regardless of whether or not they actually receive their assigned therapy (ITT) and assuming that their hospitalization and treatment discontinuation rates will be similar. Possible intercurrent events for this estimand can be, though expected to be quite rare, hospitalization (i.e., transitioning from outpatient status to inpatient status) and treatment discontinuation, both of which may lead to potential missing data or change in the primary measures. The study participants will be reminded to submit their Modified FLU-PRO Plus questionnaires even after these intercurrent events to avoid missing data as much as practically possible. Hospitalization-free, while-on-study and per-protocol treatment versions of the above estimand will also be considered within each population definitions above.

Median time to sustained clinical response for the treatment and placebo arms will be estimated using the Kaplan-Meier method and Log-rank test will be utilized to compare the time to sustained clinical response distributions between the two study arms using LIFETEST procedure in SAS Version 9.4 ® (SAS Institute, Cary, North Carolina, USA). Events will be defined as cases that attain sustained clinical response while on study and time to event will be calculated as the days from the date of symptoms onset to the date that all symptoms are below Level-2 ('A little bit') on the Modified FLU-PRO Plus questionnaire. Patients who do not attain to clinical response while on study will be censored on Day-21 or on the day they are off study before Day-21 due to other reasons.

Although all analyses will be conducted based on the intent-to-treat principle, sensitivity analyses based on the adherence to the protocol regimen will also be carried out for the primary as well as secondary objectives. Sensitivity analyses will also include hospitalization-free, while-on-study, and per-protocol treatment cohorts as described above.

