### 7.1 Missing Data and Outliers:

In this study, the primary objective is driven by data collected during the baseline visit and up to Day-21; considering the short treatment and follow-up time, missing data is expected to be minimal. We do not anticipate excessive missing values; however, missingness structure will still be analyzed as to whether or not the missingness is Missing Completely at Random (MCAR), or Missing at Random (MAR), or Not-Missing at Random (NMAR). In the event of MCAR and MAR, sensitivity analyses will be carried out by using Multiple Imputation (MI) techniques when appropriate. Specifically for the Modified FLU-PRO Plus data, Last-Value-Carried-Forward (LVCF) imputation approach will be utilized as this assessment will be for Day-1 through Day-21 and LVCF approach would be appropriate to impute intermittent missing values in these time series type data.

The data quality checks will be an ongoing effort for the study and potential outliers will be detected and resolved as much as possible while the study is ongoing. In the analysis phase, the outliers will be evaluated based on whether or not they are influential values in given statistical model a given outlier may be perfectly in line with the model built and does not necessarily mean problematic for modeling assumptions. If they are found to be influential, then possible data transformation approaches such as log-transformation will be considered.

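### Censoring of non-responders follows study status, not the last diary, so a participant who stops the diary counts as event-free on days nobody observed

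*SAP*

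**What the plan says.** - **Source of the endpoint.** SAP 3.4: "Participants will complete a daily questionnaire on Covid-19 symptoms, which will be used to determine the primary endpoint for the study". No other assessment in the plan can show a response.
- **Censoring.** SAP 5.3.2: "Patients who do not attain to clinical response while on study will be censored on Day-21 or on the day they are off study", if earlier than Day 21. Protocol 9.4.2 agrees: non-responders "will be censored on Day-21 or on the day they are off study before Day-21 due to other reasons". Neither passage mentions the last completed diary or says how the off-study day is dated.
- **Study status.** Under Protocol 7.1, stopping study drug does not end participation. Under SAP 7.2, participants with missed visits remain evaluable for the primary objective. Under Protocol 7.3, loss to follow-up requires that a person "fails to attend 3 consecutive scheduled visits (either telehealth or in person) and is unable to be contacted by the study site staff". SAP 7 adds that staff record the last contact with anyone who cannot complete the study.
- **Missing diaries.** Protocol 9.4.2 and 10.1.8 apply last-value-carried-forward (LVCF) to missing values where appropriate. SAP 7.1 applies it to the diary and justifies it for intermittent gaps. Multiple imputation is a conditional sensitivity analysis, while SAP 7.4 says that sensitivity analysis does not apply.
- **Expected losses.** SAP 3.2: "With an attrition expectation of around 20%, the planned accrual is 26 patients in each arm". SAP 7.1: "considering the short treatment and follow-up time, missing data is expected to be minimal".

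**The concern.** Kaplan-Meier estimation and the log-rank test treat each participant as observed and event-free up to the censoring date. Here that date can fall well after the last diary. The days between then count as days without response, although a response on them could not have been recorded. This needs no informative dropout: diary stopping that is purely random still makes the counted follow-up longer than the observed follow-up.

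At stake are the two medians that define the primary estimand and the log-rank comparison, in a trial of 52 to 60 people where a few participants matter. If stopping is similar in both arms, both medians lengthen and power falls. If it differs, the arm with more stopping looks slower to respond.

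**Working it through.** **1. The plan's own power figure.** Inputs from SAP 3.2: 20 per arm, medians 16 and 6 days, 5% type I error, which Protocol 9.4.1 makes two-sided. The hazard ratio under exponential times is 16/6 = 2.667. Freedman's formula with all 40 participants having an event gives z = √40 × (2.667 − 1)/(2.667 + 1) − 1.96 = 0.915, so power is 82.0% against the stated 81.5%. With follow-up ending at 21 days, expected events are 20 × (0.597 + 0.912) = 30.2, and two-sided power is about 70-77% depending on the formula. For accrual, 20/0.8 = 25 against the stated 26. The present point does not depend on these figures.

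**2. When does study status end?** Visits fall on Days 4, 7, 10, 14 and 21, with a call on Day 45.
- *Attends visits, stops the diary.* Still on study, so censored on Day 21. A diary that ends on Day 8 adds 21 − 8 = 13 unobserved days.
- *Disappears, off-study day set by the third missed visit.* Last attended visit Day 1: Day 10. Day 4: Day 14. Day 7: Day 21. Day 10: the third miss is Day 45, so censoring is on Day 21. Day 14 or later: three misses are impossible, so Day 21 again.
- *Disappears, off-study day set at last contact.* Little or no unobserved time is added.

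The first case follows directly from the text. The second depends on a date that the plan does not define.

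**3. Does LVCF repair it?** If LVCF is limited to intermittent gaps, it does not reach a diary that stops for good. If it is extended, a last diary with any score above 2 is carried to Day 21 as non-response, which is the same error. A last diary with all scores at or below 2 can instead become a three-day response that nobody observed.

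**4. Effect on the median.** Assume exponential times with rate λ = ln 2/median, and a fraction d who stop the diary at a time uniform on 0-21 days. Under Day-21 censoring the apparent survival curve is

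S(t) = (1 − d)·e^(−λt) + d·[(1 − e^(−λt))/(21λ) + (1 − t/21)·e^(−λt)].

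For a median of 16, λ = 0.0433. With d = 0.2 and t = 17.95, e^(−λt) = 0.4595, the bracket is 0.594 + 0.067 = 0.661, and S = 0.8 × 0.4595 + 0.2 × 0.661 = 0.500.

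| True median | d = 10% | d = 20% | d = 30% |
|---|---|---|---|
| 16 days | 16.9 | 17.95 | 19.4 |
| 6 days | 6.15 | 6.25 | 6.4 |

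**5. Effect on the test.** Simulation with 26 per arm, exponential times from Day 1 rounded up to whole days, stop days uniform on Days 1-20, no three-day requirement, 2,000 trials. Entries are the percentage of trials with two-sided p < 0.05.

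| Medians (placebo, TQ) | Stopping (placebo/TQ) | Complete diaries | Last-diary censoring | Day-21 censoring |
|---|---|---|---|---|
| 16, 6 | 20%/20% | 87.4 | 84.2 | 80.3 |
| 16, 6 | 10%/30% | 88.3 | 85.3 | 67.8 |
| 16, 6 | 30%/10% | 86.8 | 83.8 | 88.1 |
| 16, 16 | 20%/20% | 5.0 | 4.8 | 5.0 |
| 16, 16 | 10%/30% | 4.2 | 4.4 | 5.4 |
| 10, 10 | 0%/40% | 5.4 | 5.2 | 10.8 |

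In the first row the placebo median is not reached in 18% of trials with last-diary censoring and 26% with Day-21 censoring.

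Adding the SAP's three-day requirement, with stops on Days 2-18, gives 83% against 77-80% for 20%/20%, and 83% against 63-68% for 10%/30%. The ranges span the third-missed-visit date and Day 21. The placebo median is then not reached in 29% against 42-48% of the 20%/20% trials. A further run gave 83.7% against 80.1% with 10% stopping in both arms, and 84.1% against 82.6% with 5%.

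**The case against.** Much of the case against a stronger claim stands.

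- **Every lost participant is credited with unobserved time.** A reader might infer this from Protocol 7.3. But that section says when someone is considered lost, not which date is used, and SAP 7 has staff record the last contact. Dating exit at last contact fits the text equally well. Someone who withdraws on the day of the last diary is censored correctly.
- **The 20% attrition is the diary-stop rate.** It is not. It covers people who leave, while the firm problem concerns people who stay without diaries. SAP 7.1 expects little missing data, and SAP 5.3.2 plans reminders to keep submitting diaries after hospitalisation or treatment discontinuation.
- **The rule inflates false positives.** With equal stopping it does not. At the documents' 16-day median, even 10%/30% gave 5.4% against 4.4%. The marked inflation needs an extreme imbalance and a 10-day median that the documents do not contain.
- **The error always runs towards non-response.** LVCF on a low last diary can push it the other way.
- **The clock.** The 16 days run from symptom onset, whereas the simulations start at Day 1. If some 4 days had already passed (an assumption; 12 and 4.5 days remaining), the placebo median was not reached in 11% against 6% of trials.
- **Other analyses.** Multiple imputation and the while-on-study and per-protocol versions are planned. They are supplementary or conditional, SAP 7.4 contradicts them, and none changes the primary rule.

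None of this supplies a reason to count undocumented days as observed.

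**Conclusion.** The rule is wrong as written. For a participant who remains on study without completing diaries, both documents direct the analysis to count unobserved days as event-free. For one who disappears, the same follows if the off-study day is set by the third missed visit rather than by last contact.

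The size is conditional on a diary-stop rate that the documents do not give. Under the assumptions used (26 per arm, exponential times, 16 and 6 days from Day 1, random stopping), 10-20% stopping in both arms costs about 3-6 points of power, lengthens the placebo median and leaves it unreached more often, while type I error stays near 5%. Unequal stopping biases the comparison against the arm with more of it: 10% on placebo and 30% on TQ Formula gives power of about 63-68% against 82-85%. The reverse imbalance raised rejection from 83.8% to 88.1%, which is an artefact and not information.

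This should be fixed, but it does not invalidate the trial. The serious consequences need an imbalance that nothing in the documents predicts.

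**What to change.** Before unblinding:

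1. In SAP 5.3.2 and Protocol 9.4.2, censor each non-responder at the last day on which completed diaries allow response status to be judged, no later than Day 21, and at Day 1 if there is no post-baseline diary. Say how that day is counted under the SAP's three-day requirement, since a response that starts on day t can be confirmed only with diaries to day t + 2.
2. In SAP 7.1 and Protocol 9.4.2 and 10.1.8, limit LVCF for the diary to intermittent gaps between completed diaries, and state that nothing is carried beyond the last completed diary.
3. State the clock on which Day 21 is counted. SAP 3.2 starts time to response at the date of testing, SAP 5.3.2 and Protocol 9.4.2 at symptom onset, and the visit schedule at Day 1.
4. Keep event-free-to-Day-21 censoring as a labelled sensitivity analysis, and reconcile SAP 7.4 with it and with SAP 5.3.2 and 7.1.

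The cost is a few sentences across both documents and a small change to the derivation of the censoring date. No new data are needed.

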3. To compare the duration and severity of symptoms (measured by Modified FLU-PRO Plus) overtime from Day 1 through Day 14 in total Modified FLU-PRO Plus symptom severity score overall and in sub-domain scores (namely, Nose, Throat, Eyes, Chest/Respiratory, Gastrointestinal, Body/Systemic, Taste/Smell), between treatment with 3 g TQ Formula (500 mg per capsule, 3 capsules BID) given orally on outpatient basis and placebo in participants with COVID-19 infection	Measurement of severity of and change in Covid-19 symptoms per total score as well as sub-scores (Nose, Throat, Eyes, Chest/Respiratory, Gastrointestinal, Body/Systemic, Taste/Smell) measured through Modified FLU-PRO Plus from Day-1 through Day-14 in participants with COVID-19 infection treated either with 3 g TQ Formula (500 mg per capsule, 3 capsules BID) or placebo	FLU-PRO is a validated measure that has been used on multiple virus studies [111]. The Modified FLUPRO Plus version has additional questions (Taste/Smell) that are Covid-19 specific. The Modified FLU-PRO Plus has been shortened to reduce number of symptoms.
4. To investigate if there exists an association between viral load and symptom severity by study arm and if such associations change overtime	Correlation Coefficient of quantitative viral load and symptom severity at baseline, at Day-7, and Day-14 in participants taking 3 g TQ Formula (500 mg per capsule, 3 capsules BID) versus participants taking placebo	Decreases in viral load are hypothesized to be correlated with better clinical outcomes [109, 110].
5. To evaluate the safety and tolerability of TQ Formula (500 mg oral capsule, 3 capsules BID) when given to participants with COVID-19 infection.	Number of overall adverse events, related adverse reactions, and hospitalizations reported in participants taking 3 g TQ Formula (500 mg per capsule, 3 capsules BID) versus participants taking placebo. All AEs/SAEs will be captured throughout the study as per schedule of assessments.	Comparing the number of AEs and SAEs and any relationship to IP is important for determining the safety profile of TQ Formula.

OBJECTIVES/Purpose	ENDPOINTS/Outcome Measures	JUSTIFICATION FOR ENDPOINTS
Tertiary/Exploratory		

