8.3 ADVERSE EVENTS AND SERIOUS ADVERSE EVENTS

8.3.1 DEFINITION OF ADVERSE EVENTS (AE)

Adverse event is defined as any untoward medical occurrence associated with the use of an intervention in humans, whether or not considered intervention-related (21 CFR 312.32 (a)).

For this study, adverse events will be captured from the time of informed consent until 7 days after last dose of investigational product (30 days after last dose for SAEs)

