9.1 STATISTICAL HYPOTHESES

The primary statistical hypotheses are:

1. Treatment with 3 g TQ Formula (500 mg per capsule, 3 capsules BID) given orally on outpatient basis (study drug) will significantly reduce median time to sustained clinical response compared to placebo in participants with COVID-19 infection treated in the outpatient setting. Sustained clinical response is defined as a reduction of scores to ≤ 2 on all symptoms of the Modified FLU-PRO Plus.

The secondary statistical hypotheses are as follows:

1. Study drug will significantly reduce quantitative viral load by Day-14 compared to placebo in participants with COVID-19 infection treated in the outpatient setting.
2. Study drug will significantly increase the percentage of negative/undetectable RT-PCR viral load at Day 7 and Day 14 in participants taking 3 g TQ Formula (500 mg per capsule, 3 capsules BID) versus participants taking placebo in participants with COVID-19 infection
3. Study drug will significantly reduce duration and severity of symptoms overall and within each symptom domain overtime from Day 1 to Day 14 compared to placebo in participants with COVID-19 infection
4. There is a significantly positive correlation between quantitative viral load and symptom severity at baseline, at Day 7, and Day 14 in patients with COVID-19 infection

5. Study drug will lead to acceptable AE and SAE profiles compared to placebo

- Primary Efficacy Endpoint(s):
 1. Measurement of the difference in median time to sustained clinical response in participants taking 3 g TQ Formula (500 mg per capsule, 3 capsules BID) versus participants taking placebo.
- Secondary Efficacy Endpoint(s):
 1. Measurement of change in quantitative viral load from baseline, Day 7, and Day 14 using RTPCR in participants taking 3 g TQ Formula (500 mg per capsule, 3 capsules BID) versus participants taking placebo with COVID-19 infection.
 2. Percentage of negative/undetectable RT-PCR (i.e., viral clearance) on Day-7 and Day-14 in participants taking 3 g TQ Formula (500 mg per capsule, 3 capsules BID) versus participants taking placebo
 3. Measurement of severity of and change in Covid-19 symptoms per total score as well as sub-scores (Nose, Throat, Eyes, Chest/Respiratory, Gastrointestinal, Body/Systemic, Taste/Smell) measured through Modified FLU-PRO Plus from Day 1 through Day 14 in participants with COVID-19 infection treated either with 3 g TQ Formula (500 mg per capsule, 3 capsules BID) or placebo

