# BOSS-Covid-19 Study (BOSS-001)

Also, exploratory analyses not necessarily identified in this SAP and/or specified in the corresponding protocol may be performed, should the investigating team and/or EC deem it necessary. Any post-hoc, or unplanned analyses not identified in this SAP will be clearly identified in the respective Clinical Study Report (CSR).

The following documents were reviewed and used as guiding references in preparation of this SAP:

- Clinical Research Protocol: BOSS-001 Version 6.0 dated 17 May 2021
- ICH E9: Statistical Principles for Clinical Trials (September 1998)
- E9 Statistical Principles for Clinical Trials Guidance document by FDA

Although we have quoted the relevant sections of the protocol in this SAP for convenience, the reader of this SAP is encouraged to also read the entire clinical protocol for details on the intervention and conduct of this study, and the operational aspects of clinical assessments and their timings subjects in this study.

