# BOSS-Covid-19 Study (BOSS-001)

1. To evaluate if treatment with 3 g TQ Formula (500 mg per capsule, 3 capsules BID) given orally on outpatient basis can significantly reduce median time to sustained clinical response compared to placebo in participants with COVID-19 infection treated in the outpatient setting. Sustained clinical response is defined as a reduction of scores to </= 2 on all symptoms of the Modified FLU-PRO Plus and should be remaining </= 2 for at least three days.
2. To evaluate the safety and tolerability of TQ Formula (500 mg oral capsule, 3 capsules BID) when given to participants with COVID-19 infection

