### 5.2 Analysis Sets

The following are the main analysis datasets defined in the study protocol:

- Full Analysis Dataset: The Full Analysis Set (FAS) is defined as all randomized participants who receive at least one dose of study intervention.
- Final Dataset for Primary Objectives (FDPO): FDPO is defined as all randomized evaluable participants regardless of whether or not they received the assigned treatment regimen according to the evaluability definition above.
- Intent-to-treat (ITT) dataset: ITT dataset is defined as all randomized patients regardless of their adherence to or completion of the study regimen. This dataset includes all randomized participants even if they do not receive any dose or they withdraw from the study without completing the regimen or experience protocol violations.
- Safety Analysis Dataset: The Safety Analysis Set is defined as participants who take at least one dose of study intervention.
- Per-Protocol Analysis Dataset: The Per-Protocol Analysis Set (PP) is defined as all participants in the FAS who complete all visits up to and including Day 14, are compliant with study medication and do not have any major protocol violation. Major protocol violations will be identified prior to breaking the blind.

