Primary Estimand-2 for the safety objective is the difference of frequencies of Adverse Events and Serious Adverse Events between participants taking 3 g TQ Formula (500 mg per capsule, 3 capsules BID) and participants taking placebo regardless of whether or not they actually receive their assigned therapy (ITT) and assuming that their hospitalization and treatment discontinuation rates will be similar. The above mentioned intercurrent events are also applicable for this safety estimand. Therefore, hospitalization-free, while-on-study and per-protocol treatment versions of the above estimand will also be considered within each population definitions above.

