## **5.3.6 Safety Analyses**

Safety will be evaluated by summary of adverse events. Adverse event incidence rates will be summarized for each study arm, namely, Active Drug and Placebo Arms, in terms of severity and its relationship to study drug. A tabulation of Serious Adverse Events (SAEs) will be provided within each study arm with the number of patients experiencing a given AE or ADE, and the number of episodes while on study. Similar reports will be generated for AE monitoring purposes for the entire study cohort without unblinding of the study participants while the study is still ongoing.

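### The SAP's lead safety comparison uses all randomised participants, has no post-first-dose counting rule, and has no interval or criterion from which acceptable safety could be concluded

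*SAP*

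**What the plan says.** **Level of the objective.** SAP 3.6 lists safety as the second primary objective: "To evaluate the safety and tolerability of TQ Formula (500 mg oral capsule, 3 capsules BID) when given to participants with COVID-19 infection". Protocol section 3 lists it as secondary objective 5, and protocol 9.4.3 analyses it among the secondary endpoints.

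**Population.** SAP 5.3.2 sets Primary Estimand-2 as the difference in AE and SAE frequencies between TQ Formula participants and "participants taking placebo regardless of whether or not they actually receive their assigned therapy (ITT"). SAP 5.2 states that the ITT set keeps randomised people who receive no dose. The same section says: "The Safety Analysis Set is defined as participants who take at least one dose of study intervention". Neither SAP 5.3.2 nor SAP 5.3.6 names that set. SAP 5.3.2 adds hospitalisation-free, while-on-study and per-protocol versions of the estimand within the populations defined earlier.

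**Events.** Protocol 8.3.1 says "adverse events will be captured from the time of informed consent until 7 days after last dose of investigational product" (30 days for SAEs). Neither document defines a treatment-emergent AE.

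**Analysis and hypothesis.** SAP 5.3.6 opens with "Safety will be evaluated by summary of adverse events" and describes summaries by arm. Protocol 9.4.3 adds Fisher's exact test where frequencies permit. Protocol 9.1 states the hypothesis as "Study drug will lead to acceptable AE and SAE profiles compared to placebo". No confidence interval, margin or other criterion for the between-arm comparison appears in either document.

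**The concern.** In a safety comparison, anything that pulls the arms together hides harm. Never-dosed participants cannot have a drug effect, and events before first dose cannot be caused by the drug. Counting either adds the same kind of noise to both arms and shrinks a real excess. The SAP defines a set of dosed participants and then leads with a different one.

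The second problem is the step from data to conclusion. The estimand is a difference, but the SAP's outputs are arm-by-arm summaries, and the only comparative tool in either document is a conditional significance test. The protocol hypothesises an acceptable profile without saying what result would count as one. With 26 to 30 per arm, a report could end with no significant difference and be read as reassurance that the data do not give.

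**Working it through.** **Plan's own figure.** There is none for safety. The only power figure, 81.5% with 20 per arm, belongs to the efficacy endpoint, and SAP 3.2 bases power on the first primary objective alone.

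**Inputs from the documents.** 26 to 30 per arm (SAP 3.2); two-sided 0.05 (protocol 9.4.1); screening on Day -3 to -1, which may be combined with baseline (protocol 1.3); 14 days of dosing; collection to 7 days after last dose, or 30 days for SAEs (protocol 8.3.1).

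**Assumed inputs.** The documents give no AE or SAE rates and no expected number of never-dosed participants. All such values below are illustrative.

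**1. Never-dosed participants in the denominator.** Take a true 30% rate among the dosed, no events in the never-dosed, and 26 randomised to the arm.
- One never dosed: 0.30 × 25/26 = 28.8%
- Two never dosed: 0.30 × 24/26 = 27.7%

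For the difference, take 30% v 10% with never-dosed participants at the 10% background rate. The 20-point difference becomes 20 × (1 − u) for a never-dosed share u: 19.6, 19.0 and 18.0 points at u = 2%, 5% and 10%.

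**2. Pre-dose days.** With d pre-dose days, the pre-dose share of the non-serious AE window is d/(d + 14 + 7).
- d = 0: 0%
- d = 1: 1/22 = 4.5%
- d = 3: 3/24 = 12.5%

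For SAEs the maximum is 3/(3 + 14 + 30) = 3/47 = 6.4%. With a constant background rate, a true rate ratio of 2.0 over the 21 days after first dose becomes (d + 42)/(d + 21): 43/22 = 1.95 for d = 1 and 45/24 = 1.88 for d = 3.

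**3. What Fisher's test can show.** Power is the sum, over all pairs of counts with p ≤ 0.05, of the two binomial probabilities multiplied together.

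| Assumed rates | 26 per arm | 30 per arm |
|---|---|---|
| 20% v 40% | 25.0% | 29.8% |
| 10% v 20% | 9.2% | 9.6% |
| 5% v 15% | 8.1% | 9.3% |

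At 26 per arm, 5 v 0 patients gives p = 0.051, so at least 6 v 0 is needed for significance.

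**4. What an interval would show.** With zero events, the upper limit of the two-sided 95% exact interval is 1 − 0.025^(1/n): 13.2% for n = 26 and 11.6% for n = 30. For equal observed AE rates of about 10% to 50%, the Newcombe 95% interval for the risk difference is about ±19 to ±25 points at 26 per arm and ±17 to ±24 at 30.

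**5. Hospitalisation.** SAP 4.2 counts hospitalisations as a safety endpoint, and protocol 8.3.2 makes inpatient hospitalisation a criterion for an SAE. Primary Estimand-2 nevertheless assumes similar hospitalisation rates in the two arms and adds a hospitalisation-free version. The assumption takes for granted part of what is to be estimated, and the extra version removes those events.

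**The case against.** Several stronger readings are tempting, and the documents do not support them.

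- **That the SAP ignores dosed participants.** It does not. SAP 5.3.2 adds versions of the safety estimand within the defined populations. Where SAP 5.3.3 spells that phrase out for the first secondary estimand, it names the Full Analysis Set, which among randomised people is the same group as the Safety Analysis Set. What stands is that the dosed-only analysis is supplementary and the Safety Analysis Set is assigned to no analysis.
- **That events are counted from consent.** Protocol 8.3.1 sets a collection window, which is proper in itself. Conditions present at screening are medical history (protocol 8.3.4), the pre-dose window can be zero, and attribution to study drug should largely keep pre-dose events out of the related-AE tables. What stands is the missing counting rule for all-cause AEs.
- **That the SAP promoted safety to primary.** The SAP cites "Clinical Research Protocol: BOSS-001 Version 6.0 dated 17 May 2021", its eligibility text differs from the supplied protocol, and protocol 9.4.1 itself mentions two primary objectives. The difference may come from another protocol version. What stands is that the supplied documents disagree.
- **That a non-significant test is the planned route to acceptable safety.** No section says so. Fisher's test is conditional, SAP 5.3.6 is descriptive, and the one explicit safety rule is a count in the first 12 patients. What stands is that no route is given at all.
- **That adding an interval would cure this.** Without a margin, it would not.

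**Conclusion.** The point holds in this form: the lead population for the safety estimand is the wrong one for its purpose, the counting rule is missing, and no interval or criterion links the data to a conclusion about acceptability.

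The population and window effects are modest. They amount to one or two percentage points on an assumed 30% rate with one or two never-dosed in 26, and at most 12.5% of the non-serious AE window. Both go in the direction that understates harm. The sample size and the absent criterion matter more: 25% power for an assumed doubling from 20% to 40%, and 8% for an assumed tripling from 5% to 15%, at 26 per arm. A non-significant result is therefore expected even with a real excess of that size and would not show acceptable safety. The sizes rest on assumed event rates and never-dosed counts; the textual gaps do not. The conflict over the level of the objective is real, but its cause cannot be settled from these documents.

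**What to change.** In SAP 5.3.2 and 5.3.6:

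1. Make the Safety Analysis Set, by treatment actually taken, the lead population for Primary Estimand-2. SAP 5.2 should state the by-treatment-taken rule, which its definition now lacks.
2. Count events with onset on or after first dose in the between-arm comparison, and list pre-dose events separately.
3. Report risk differences with 95% confidence intervals for any AE, related AE, Grade 3+ AE, SAE and hospitalisation.
4. For this estimand, delete the assumption of similar hospitalisation rates and the hospitalisation-free version.
5. Describe the safety conclusion as descriptive, and do not present an acceptable profile as something the trial has shown.

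Across the current protocol and SAP, reconcile whether safety is a primary or secondary objective. The documents supplied do not settle which is intended.

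The cost is SAP wording and slightly more analysis work, with no new data. The sponsor gives up a formal safety claim that 26 to 30 per arm could not support.
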